8.6.3 Summaries of Demographic and Baseline Characteristics

The comparability of the treatment groups for each relevant characteristic will be assessed by the use of tables and/or graphs. No statistical hypothesis tests will be performed on these characteristics. The number and percentage of subjects screened and randomized, and the primary reasons for screening failure and discontinuation will be displayed. Demographic variables (e.g., age), baseline characteristics, primary and secondary diagnoses, and prior and concomitant therapies will be summarized by treatment either by descriptive statistics or categorical tables.

8.7 Interim Analyses

There are 2 planned interim analyses for OS and 1 planned interim analysis for PFS in this trial. Results of the interim analyses will be reviewed by an eDMC. Table 20 shows analysis strategies for each interim and final analysis in this trial based on model assumptions. Table 20 will be updated using the actual number of events at the interim and final analyses and the same spending function used to derive the design in this table. All futility boundaries are non-binding in this study.

Table 20 Summary of Interim and Final Analyses Strategies

Analysis	Expected Months after Study Start	Hypothesis Tested in the Analysis	True Hazard Ratio	n [†]	Information Fraction	Type I Error (Overall α)	Efficacy Boundary Crossing				Futility Boundary Crossing			
							Nominal α	Z-value	Statistics [‡]	Power [§]	Nominal α	Z-value	Hazard Ratio	Cumulative Type II Error
IA1	22 Months	PFS	0.6	365	0.75	0.20%	0.11%	3.06	0.73	~96.5%	22.1%	-0.77	1.08	<0.01%
						1.35%	0.74%	2.44	0.77	~99.2%	21.8%	-0.78	1.08	<0.01%
						2.5%	1.36%	2.21	0.79	~99.6%	21.6%	-0.79	1.08	<0.01%
		OS	0.75	195	0.48	2.3%	0.01%	3.72	0.59	~4.3%	4.1%	-1.74	1.28	~0.01%
						2.5%	0.01%	3.70	0.59	~4.5%	4.1%	-1.74	1.28	~0.01%
						0.2%	0.2%	2.88	9.4%	>99.9%	-	-	-	-
ORR	-	860	1.0	1.15%	1.15%	2.27	7.4%	>99.9%	-	-	-	-		
				2.5%	2.5%	1.96	6.4%	>99.9%	-	-	-	-		
				0.2%	0.14%	3.00	0.76	>99.9%	99.8%	3.00	0.76	~3.9%		
IA2	31 Months	PFS	0.6	487	1.0	1.35%	1.02%	2.32	0.81	>99.9%	98.7%	2.32	0.81	~0.04%
						2.5%	1.95%	2.06	0.83	>99.9%	97.5%	2.06	0.83	~0.02%
						2.3%	0.78%	2.42	0.76	~52.7%	20.3%	-0.84	1.10	~0.05%
		OS	0.75	299	0.74	2.5%	0.92%	2.36	0.76	~55.1%	20.2%	-0.85	1.10	~0.05%
						2.3%	2.07%	2.04	0.82	~80.8%	97.7%	2.04	~0.82	~19.2%
						2.5%	2.22%	2.01	0.82	~81.7%	97.5%	2.01	~0.82	~18.3%
FA	43 Months	OS	0.75	404	1.0	2.3%	2.07%	2.04	0.82	~80.8%	97.7%	2.04	~0.82	~19.2%
						2.5%	2.22%	2.01	0.82	~81.7%	97.5%	2.01	~0.82	~18.3%

[†] n means expected events at the time of corresponding analysis for PFS and OS based on model assumption. In the rare case if PFS events accumulate slower than expected, a minimum of 305 events is required at 22 months to trigger IA1; n means total sample size for ORR.

[‡] The statistics used here are hazard ratio for PFS and OS, and ORR Δ for ORR where ORR Δ = ORR in (pembrolizumab+axitinib group) – ORR in sunitinib group.

[§] The power calculated for OS is cumulative power. For the power calculation, the target ORR in the pembrolizumab+axitinib group and the reference ORR assumed in the sunitinib groups are 55% and 31%, respectively.

For OS, a linear spending function with a fixed alpha spending of 0.0001 at IA1 and the rest alpha spending approximated by a Hwang-Shih-DeCani (HSD) alpha-spending function with gamma parameter (-4) is used to construct Haybittle-Peto type of group sequential boundaries to control the overall Type I error rate for this endpoint at 2.3% or 2.5% (1-sided). Futility spending is done by controlling the probability of crossing the futility bound under the null hypothesis (total of $1-\alpha=97.5%$); an HSD alpha-spending function with gamma parameter (-6) is used to construct group sequential boundaries for futility. The Type I error rate to spend at IA2 and FA will be determined by the spending function evaluated at the exact number of deaths at each analysis.

For PFS, an HSD alpha-spending function with gamma parameter (-2), is used to construct group sequential boundaries to control the overall Type I error rate for this endpoint at 0.2%, 1.35% and 2.5% (1-sided). Futility spending is done by controlling the probability of crossing the futility bound under the null hypothesis (total of $1-\alpha=97.5%$); an HSD alpha-spending function with gamma parameter (-6) is used to construct group sequential boundaries for futility. The Type I error rate to spend at the interim analysis will be determined by the spending function evaluated at the exact number of PFS events at each analysis.

For ORR, if the testing of ORR hypothesis does not reach statistical significance at interim analysis 1 (IA1), the p-value from the IA1 analysis can be compared to an updated α -level if the null hypothesis for PFS or OS is rejected at a later time.

The purpose of the first interim analysis is to conduct the interim testing for efficacy on both PFS and OS endpoints. It will be performed after enrollment completion, which is expected after 15 months since start of the study. The IA1 data cutoff is to occur once a minimum of 305 PFS events have accrued and all patients have been followed up for at least 7 month after randomization. A minimum of 305 PFS events will ensure at least 90% power for the PFS analysis at IA1. The minimum follow-up time requirement is to ensure sufficient follow up for the PFS endpoint to characterize the PFS curves at the tail and ensure sufficient follow up for the ORR endpoint for this interim analysis. Based on fulfilling these two criteria for IA1, IA1 is projected to happen at approximately 22 months after the start of the study with approximately 365 PFS events based on model assumptions (see [Table 20](#)). In the unexpected case that there are fewer than 305 PFS events when all subjects have had the opportunity to be followed up for at least 7 months after randomization, the interim analysis will be delayed until 305 PFS events have accrued.

The second interim analysis is to conduct the final analysis for the PFS endpoint if the superiority of PFS has not been demonstrated in the first interim analysis and to conduct the second interim testing of the OS endpoint. It will be performed when approximately 74% of the final required OS events (or 299 deaths) have accrued, expected after 31 months from the start of the study. It is expected to accumulate 487 PFS events at that time.

The final analysis for the study will be conducted when the target number of OS events (404 deaths) is reached, projected to occur at 43 months after the start of the study, if the study has not been stopped early for efficacy.

In the first interim analysis, if the study demonstrates superiority of PFS but has not demonstrated superiority of OS (without crossing the futility boundary for OS), the study will continue for OS after the interim analysis.

If superiority of pembrolizumab in combination with axitinib relative to sunitinib with respect to PFS or OS is demonstrated, the ORR hypothesis will be tested using the p-value from the first interim analysis with the overall Type I error $\alpha = 0.2\%$, 1.15% , or 2.5% , depending on the results of the OS and PFS hypothesis tests. Since all subjects will have an opportunity to have at least 4 scheduled scans at the time of the first interim analysis if not discontinued prior to the first interim analysis data cut-off, they all will be included in this ORR analysis.

The DMC has responsibility for assessment of overall risk: benefit. The DMC will review safety periodically (every 4 months in the first year and frequency may be reduced after one year if no unexpected safety signals occur). To account for any multiplicity concerns raised by the DMC review of unplanned efficacy data when prompted by safety concerns, a sensitivity analysis for OS will be pre-specified in the sSAP. This analysis will be performed if requested by the DMC. However, DMC review of OS data beyond the planned efficacy analysis to assess the overall risk:benefit to trial participants will not require multiplicity assessment typically associated with a planned efficacy interim analysis because these analyses are not to declare a positive efficacy finding. Any DMC recommendation will be communicated to the Sponsor as agreed to in the DMC charter. A detailed description of the multiplicity adjustment and hypotheses testing plan is provided in Section 8.8 Multiplicity.

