OS Hypothesis: The OS hypothesis may be tested at $\alpha=2.3\%$ (initially allocated α) or at $\alpha=2.5\%$ (if both the ORR and PFS null hypotheses are rejected). The nominal Type I error rates for the interim analysis and final analysis that will allow tight control of the overall Type I error for testing the OS hypothesis will be derived using the alpha-spending function approach based on the overall Type I error allocated to the OS hypothesis. The group sequential testing of the OS hypothesis will use a linear α -spending function with a fixed α -spending of 0.0001 at IA1 and the rest α -spending approximated by an HSD α -spending function with $\gamma=-4$ to construct Haybittle-Peto type of group sequential boundaries to control the overall Type I error rate for this endpoint at 2.3% or 2.5% (1-sided). The futility spending is done by controlling the probability of crossing the futility bound under the null hypothesis (total of $1-\alpha=97.5\%$); an HSD alpha-spending function with $\gamma=-6$ is used to construct group sequential boundaries for futility. The boundary thresholds will be updated using the actual number of OS events at the interim and final OS analyses and the same spending function used to derive the design.

ORR Hypothesis: The ORR hypothesis will be tested with all subjects, since all subjects will have “mature ORR information,” with an opportunity to complete 4 scheduled scans at the first interim analysis. The ORR hypothesis is initially allocated a Type I error $\alpha=0\%$ and thus, cannot be tested unless one or both of the PFS or OS null hypotheses have been rejected. Depending on the results of the OS and PFS hypotheses testing, the ORR hypothesis can be tested at an overall Type I error levels of $\alpha=0.2\%$, 1.15%, or 2.5%. If the testing of ORR hypothesis does not reach statistical significance at interim analysis 1 (IA1), the p-value from the IA1 analysis can be compared to an updated α -level if the null hypothesis for PFS or OS is rejected at a later time. [Table 20](#) shows the boundary thresholds of the ORR hypothesis at each of these Type I error levels.

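### Table 20's OS efficacy bounds at overall alpha 2.5% do not follow the one OS spending function stated for both alpha levels; settle this before IA2

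*Combined protocol and SAP*

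**What the plan says.** Section 8.7, under Table 20, describes OS spending as "a linear spending function with a fixed alpha spending of 0.0001 at IA1", with "the rest alpha spending approximated by a Hwang-Shih-DeCani (HSD) alpha-spending function with gamma parameter (-4"), used "to control the overall Type I error rate for this endpoint at 2.3% or 2.5% (1-sided"). Section 8.8 repeats the same rule for the same two levels. Neither section gives a separate function for 2.5%. Section 8.8 moves OS from 2.3% to 2.5% "if both the ORR and PFS null hypotheses are rejected".

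Two sentences in Section 8.7 say how the bounds will be set in practice. One reads: "The Type I error rate to spend at IA2 and FA will be determined by the spending function evaluated at the exact number of deaths". The other says that Table 20 will be updated with the actual event counts "and the same spending function used to derive the design in this table".

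The OS efficacy entries in Table 20 (nominal one-sided alpha / Z / cumulative power) are:

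| Overall alpha | IA1, 195 deaths | IA2, 299 deaths | FA, 404 deaths |
|---|---|---|---|
| 2.3% | 0.01% / 3.72 / 4.3% | 0.78% / 2.42 / 52.7% | 2.07% / 2.04 / 80.8% |
| 2.5% | 0.01% / 3.70 / 4.5% | 0.92% / 2.36 / 55.1% | 2.22% / 2.01 / 81.7% |

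**The concern.** An HSD spend is the overall alpha multiplied by a fraction that depends only on the information fraction and gamma. With one function and the same death counts, the share of alpha used by IA2 should therefore be the same in both OS rows. In the printed table it is not: IA2 uses about 34% of alpha in the 2.3% row and about 37% in the 2.5% row.

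The stake is a decision threshold on a primary endpoint. Table 20 gives PFS about 96.5% power at IA1 and ORR more than 99.9%, so under the design assumptions OS will most likely be tested at 2.5% by IA2. If text and table give different bounds at that level, a result between them has no pre-specified answer. The promised update does not settle this by itself. It points to the function behind the table, and for the 2.5% rows that is not the function in the text.

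**Working it through.** **Inputs.** Deaths 195 / 299 / 404 and true HR 0.75 (Table 20, Section 8.9); 1:1 allocation (Section 8.9); futility non-binding, so ignored for the efficacy bounds (Section 8.7); spend 0.0001 at IA1, then HSD with gamma -4.

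**Formulas.** HSD fraction h(t) = (1 - exp(-gamma t)) / (1 - exp(-gamma)). Cumulative spend is 0.0001 at IA1, alpha x h(299/404) at IA2, and alpha at FA. Bounds are found by recursive numerical integration with information = deaths/4. Boundary HR = exp(-2Z / sqrt(deaths)).

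h(299/404) = (exp(2.9604) - 1) / (exp(4) - 1) = 0.3415. Cumulative spend at IA2 is then 0.023 x 0.3415 = 0.00786, or 0.025 x 0.3415 = 0.00854.

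**Step 1: reproduce the 2.3% rows.** Z 3.719 / 2.416 / 2.039; nominal 0.010% / 0.78% / 2.07%; power 4.4% / 52.8% / 80.9%. These match Table 20, with power within 0.1 point. So the reading of the text and the method are both sound.

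**Step 2: apply the same rule at 2.5%.**

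| | IA1 | IA2 | FA |
|---|---|---|---|
| Z, derived (printed) | 3.719 (3.70) | 2.385 (2.36) | 2.003 (2.01) |
| Nominal alpha | 0.010% (0.01%) | 0.853% (0.92%) | 2.259% (2.22%) |
| Boundary HR | 0.587 (0.59) | 0.759 (0.76) | 0.819 (0.82) |
| Cumulative power | 4.4% (4.5%) | 54.1% (55.1%) | 81.9% (81.7%) |

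**Step 3: work back from the printed IA2 levels.** With 0.0001 at IA1, nominal 0.78% means a cumulative spend of 0.00781, and 0.00781 / 0.023 = 34.0%. Nominal 0.92% means 0.00921, and 0.00921 / 0.025 = 36.8%. Over the rounding range of each printed value, the 2.3% row needs gamma between -4.05 and -4.00, and the 2.5% row between -3.70 and -3.66. No single gamma serves both.

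**Step 4: try to close the gap at 2.5%.**
- Rounding of deaths: 297 / 298 / 299 / 300 deaths give 0.835 / 0.844 / 0.853 / 0.862% at IA2. About 306 deaths would be needed to reach 0.92%.
- HSD applied to alpha minus 0.0001, plus 0.0001: 0.860%.
- IA1 spend scaled to 0.0001 x 2.5/2.3 = 0.000109: Z at IA1 becomes 3.698, as printed, but IA2 stays at 0.853%.

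**Step 5: control check on PFS.** HSD with gamma -2 at 365 and 487 events gives Z 3.065 / 2.996 at 0.2%, 2.440 / 2.321 at 1.35%, and 2.208 / 2.064 at 2.5%. Table 20 prints 3.06 / 3.00, 2.44 / 2.32 and 2.21 / 2.06. The mismatch is specific to the 2.5% OS rows.

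**Step 6: consequence.** The printed 2.5% bounds (3.70 / 2.36 / 2.01) spend 0.011%, 0.915% and 2.496% cumulatively, so they do not inflate Type I error. Mixing sources would: the printed IA2 level of 0.92% followed by the text-derived final Z of 2.003 totals about 2.53%. Under HR 0.75, the chance that OS falls in the disputed window by IA2 is 55.2% - 54.1% = 1.1 points.

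**The case against.** The text does not say exact HSD. It speaks of a linear function and of an approximation to HSD, which could mean a piecewise-linear function with nodes chosen near HSD, perhaps separately for each alpha level. An IA1 node scaled with alpha and an IA2 node of 0.367 to 0.37 of alpha do give Z of about 3.70 / 2.36 / 2.01 at 2.5%. Also, the table holds planning values that will be recalculated at the actual deaths, and the numerical consequence is slight.

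The last two points are fair as to size. The first shows that the printed 2.5% rows can arise from some function, but it does not rescue the plan. The text states one rule for both levels, and an IA2 node of 0.37 applied at 2.3% would give a nominal 0.85%, not the printed 0.78%. If the nodes differ by alpha level, the documents do not say so. Recalculation does not help until it is clear which function is to be recalculated. What stands is that the sponsor may have intended something other than exact HSD at 2.5%, so stating that function is an acceptable alternative to replacing the numbers.

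**Conclusion.** The concern holds. The 2.5% OS rows of Table 20 are inconsistent with the stated spending function and with the 2.3% rows beside them. The documents do not show the cause.

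The effect is small: 0.07 percentage points of nominal alpha at IA2 (0.92% against 0.853%), 0.04 in the other direction at FA (2.22% against 2.26%), about 0.002 in the IA2 boundary HR, and about 1 point of IA2 power. Type I error is protected if either set of bounds is used throughout. The roughly 80% power at 2.3% and the event targets are unaffected.

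The derived values assume exactly 195, 299 and 404 deaths, non-binding futility and HSD with gamma -4 as stated. It should be fixed because it leaves a primary-endpoint threshold with two possible values at the alpha level most likely to apply.

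**What to change.** Before IA2, and before any OS results are seen:

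1. Recompute the 2.5% OS rows of Table 20 with the stated function. IA2: 0.85%, Z 2.39, HR 0.76, cumulative power about 54.1%. FA: 2.26%, Z 2.00, HR 0.82, power about 81.9%, Type II error about 18.1%. If a different function or set of nodes was intended, write it into Sections 8.7 and 8.8 for each alpha level instead.
2. Say in both sections that this function, evaluated at the actual deaths, governs the IA2 and final bounds.
3. State whether the IA1 spend stays at 0.0001 at both levels (Z 3.72 in both rows) or scales with alpha (0.000109 and Z 3.70 at 2.5%, as printed).

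The cost is a few table cells and a clarifying sentence in Sections 8.7 and 8.8. Deaths, sample size and analysis timing stay as they are.

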8.8 Multiplicity

The multiplicity strategy specified in this section will be applied to the 2 primary hypotheses (superiority of the pembrolizumab+axitinib combination relative to sunitinib on PFS or OS) and the secondary hypothesis of superiority of pembrolizumab+axitinib combination relative to sunitinib in ORR. Note that the study will be a success if either PFS or OS is demonstrated to be statistically significant under multiplicity control.

The overall Type I error across the testing of the OS, PFS, and ORR hypotheses is strongly controlled at $\alpha=2.5\%$ (1-sided). The multiplicity strategy will follow the graphical approach of Maurer and Bretz. Figure 5 provides the multiplicity strategy diagram of the study.

[figure not shown]

Figure 5 Multiplicity Strategy

The alpha level indicated for each null hypothesis is the alpha level initially allocated. When a particular null hypothesis is rejected, the arrows leading to it are removed and the alpha allocated to the null hypothesis will be re-distributed among all arrows going out and re-weighted per the number on the arrow (summing to 1). The arrows on the diagram show how the Type I error allocated to a hypothesis that was successfully tested will be re-distributed for the testing of the other two hypotheses. Initially, $\alpha=2.3\%$ (23/25 of the overall total $\alpha=2.5\%$ for testing the OS, PFS and ORR) is allocated to the OS hypothesis and $\alpha=0.2\%$ (2/25 of the overall total $\alpha=2.5\%$) is allocated to the PFS hypothesis.

The testing of the OS, PFS, and ORR will proceed as follows.

PFS Hypothesis: The study allocates $\alpha=0.2\%$, one-sided, to test PFS hypothesis initially. If the null hypothesis for OS is rejected, Figure 5 shows that half of its $\alpha=2.3\%$ will be reallocated to PFS hypothesis testing ($\alpha=1.35\%$). If null hypotheses for OS and ORR are both rejected, all α will be reallocated to test PFS hypothesis ($\alpha=2.5\%$). Thus, the PFS null hypothesis may be tested at $\alpha=0.2\%$, 1.35% or 2.5%. Table 20 shows the boundary thresholds corresponding to a successful group sequential testing of the PFS hypothesis at each of these Type I error levels. For PFS, the information fraction at interim analysis will be based on the final planned number of 487 events. A Hwang-Shih-DeCani (HSD) spending function with $\gamma = -2$ (α -spending for efficacy) is used to set efficacy bounds. The futility spending is done by controlling the probability of crossing the futility bound under the null hypothesis (total of 1-

$\alpha=97.5\%$); an HSD alpha-spending function with $\gamma=-6$ is used to construct group sequential boundaries for futility. The boundary thresholds at the interim analysis will be determined by the spending function evaluated at the exact number of PFS events at each analysis. Note that if the α -reallocation from OS hypothesis testing occurs at the final analysis after hypothesis testing for PFS has been completed, the previously computed PFS test statistic for the PFS analysis may be re-evaluated versus the updated bounds.

OS Hypothesis: The OS hypothesis may be tested at $\alpha=2.3\%$ (initially allocated α) or at $\alpha=2.5\%$ (if both the ORR and PFS null hypotheses are rejected). The nominal Type I error rates for the interim analysis and final analysis that will allow tight control of the overall Type I error for testing the OS hypothesis will be derived using the alpha-spending function approach based on the overall Type I error allocated to the OS hypothesis. The group sequential testing of the OS hypothesis will use a linear α -spending function with a fixed α -spending of 0.0001 at IA1 and the rest α -spending approximated by an HSD α -spending function with $\gamma=-4$ to construct Haybittle-Peto type of group sequential boundaries to control the overall Type I error rate for this endpoint at 2.3% or 2.5% (1-sided). The futility spending is done by controlling the probability of crossing the futility bound under the null hypothesis (total of $1-\alpha=97.5\%$); an HSD alpha-spending function with $\gamma=-6$ is used to construct group sequential boundaries for futility. The boundary thresholds will be updated using the actual number of OS events at the interim and final OS analyses and the same spending function used to derive the design.

ORR Hypothesis: The ORR hypothesis will be tested with all subjects, since all subjects will have “mature ORR information,” with an opportunity to complete 4 scheduled scans at the first interim analysis. The ORR hypothesis is initially allocated a Type I error $\alpha=0\%$ and thus, cannot be tested unless one or both of the PFS or OS null hypotheses have been rejected. Depending on the results of the OS and PFS hypotheses testing, the ORR hypothesis can be tested at an overall Type I error levels of $\alpha=0.2\%$, 1.15%, or 2.5%. If the testing of ORR hypothesis does not reach statistical significance at interim analysis 1 (IA1), the p-value from the IA1 analysis can be compared to an updated α -level if the null hypothesis for PFS or OS is rejected at a later time. [Table 20](#) shows the boundary thresholds of the ORR hypothesis at each of these Type I error levels.

8.9 Sample Size and Power Calculations

The study will randomize subjects in a 1:1 ratio into the experimental arm of pembrolizumab+axitinib and the control arm of sunitinib. Both PFS and OS are primary endpoints for this study. The sample size was planned for 840 but the following power calculations are based on the actual final number of randomized subjects (N = 861).

For the PFS endpoint, based on a target number of 487 PFS events and one interim analysis at approximately 75% of the target number of events, the study has ~99% power to detect an HR of 0.60 (pembrolizumab+axitinib combination versus sunitinib) at $\alpha=0.2\%$ (1-sided). The calculation assumes an HSD α -spending function with $\gamma=-2$ to control the overall Type I error rate for this endpoint at 0.2% (1-sided). The target numbers of PFS events for the first interim and final analysis are projected to occur at 22 and 31 months respectively.

For the OS endpoint, based on a target number of 404 final OS events and 2 interim analyses (with approximately 48% of final OS events at IA1 and 74% of the final OS events at IA2), the

study has approximately 80% power to detect an HR of 0.75 at an overall alpha level of 2.3% (1-sided). The calculation assumes that a linear α -spending function with a fixed α -spending of 0.0001 at IA1 and the rest α -spending approximated by an HSD α -spending function with $\gamma=-4$ to control the overall Type I error rate for this endpoint at 2.3% (1-sided). The target number of OS events is projected to occur at 43 months after the start of the study. The target numbers of OS events for the first and second interim analyses are projected to occur at 22 months and 31 months respectively.

The above calculations assume an exponential distribution with a median of 13 months for PFS and a median of 33 months for OS for the control group respectively, a yearly dropout rate of 10% for PFS and 1% for OS, and an enrollment of 15 months, with monthly accrual of 40 to 60 patients in the first 3 months and monthly accrual of ~60 patients after the first 3 months. The median PFS and median OS assumptions in the control group are based on emerging data of sunitinib from the CheckMate 214 study (59).

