
Interim and Final Analyses
	
Two interim analyses are planned for the study. Results will be reviewed by an external data monitoring committee (eDMC). Details are provided in Section 8.7.
 
 • First Interim Analysis (IA1) 
 ○ Timing: To be performed after enrollment completion, once a 7-month minimum follow up (ie, 7 months since last subject is randomized) has been achieved and a minimum of 305 PFS events have accrued. It is expected to be 22 months after the first subject randomized (study start). Approximately 48% of the final required OS events (or 195 deaths) are expected at that time. ○ Purpose: First interim analysis for PFS and OS. • Second Interim Analysis (IA2) 
 ○ Timing: To be performed when approximately 74% of the final required OS events (or 299 deaths) have accrued, expected to be 31 months after study start. At IA2, approximately 487 PFS events are expected. ○ Purpose: Final analysis for PFS and IA2 for OS. • Final analysis (event-driven trial) 
 ○ Timing: When approximately 404 deaths have accrued, expected to be 43 months after study start. ○ Purpose: Final analysis for OS (assuming not declared successful at the interim analysis)

Multiplicity
	
The overall Type I error rate is strongly controlled at 2.5% (1-sided) with 0.2% initially allocated to PFS and 2.3% initially allocated to OS. A group sequential approach will be used to allocate alpha between the interim and final analyses. The study will be considered a success if either PFS or OS is demonstrated to be statistically significant under multiplicity control. Note that the study would continue for OS even if PFS is shown to be statistically significant at IA1 or IA2.

Sample Size and Power
	
The sample size was planned for 840 but the following power calculations are based on the actual final number of randomized subjects (N = 861). There are 2 primary endpoints for this study, PFS, and OS. The expected median PFS time in the control group is 13 months. Based on 487 PFS events, the study has ~99% power to detect a hazard ratio of 0.60 for PFS (pembrolizumab+axitinib combination vs. sunitinib) at alpha=0.2% (1-sided). The expected median OS time in the control group is 33 months. Based on 404 death events, the study has 80% power to detect a hazard ratio of 0.75 for OS at alpha=2.3% (1-sided).

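### Table 20's final PFS row at alpha 0.2% contradicts itself: power >99.9% beside Type II error ~3.9%, where the stated design gives about 99.6% and 0.4%

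*Combined protocol and SAP*

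**What the plan says.** Section 8.8 sets the starting level for PFS: "The study allocates $\alpha=0.2\%$, one-sided, to test PFS hypothesis initially". Section 8.9 describes the design as "based on a target number of 487 PFS events and one interim analysis at approximately 75% of the target number of events" and concludes that "the study has ~99% power to detect an HR of 0.60". Section 8.1 repeats it: "Based on 487 PFS events, the study has ~99% power to detect a hazard ratio of 0.60 for PFS".

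Section 8.7 introduces the detailed table: "Table 20 shows analysis strategies for each interim and final analysis in this trial based on model assumptions". Its final-analysis rows for PFS (at IA2, true HR 0.6) and OS (at FA, true HR 0.75) read:

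| Endpoint | Overall alpha | Efficacy Z | Futility Z | Power | Cumulative Type II error |
|---|---|---|---|---|---|
| PFS, 487 events | 0.2% | 3.00 | 3.00 | >99.9% | ~3.9% |
| PFS, 487 events | 1.35% | 2.32 | 2.32 | >99.9% | ~0.04% |
| PFS, 487 events | 2.5% | 2.06 | 2.06 | >99.9% | ~0.02% |
| OS, 404 events | 2.3% | 2.04 | 2.04 | ~80.8% | ~19.2% |
| OS, 404 events | 2.5% | 2.01 | 2.01 | ~81.7% | ~18.3% |

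A footnote states that the OS power is cumulative; it is silent on PFS.

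**The concern.** In each final row the efficacy and futility bounds coincide, so the trial either rejects or fails to reject and no third outcome exists. Cumulative power and cumulative Type II error are then complements. The two OS rows sum to 100.0% (80.8 + 19.2 and 81.7 + 18.3), and the PFS rows at 1.35% and 2.5% are compatible with 100%. The PFS row at 0.2% is not: more than 99.9 plus 3.9 is more than 103. A Type II error of 3.9% would mean 96.1% power.

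The row matters because 0.2% is the level at which PFS is tested first, and sections 8.1 and 8.8 allow the study to succeed on PFS alone. Anyone reading the chance of missing a true HR of 0.60 from this row finds either under 0.1% or 3.9%.

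**Working it through.** **Inputs.** Allocation 1:1 (section 8.9: "The study will randomize subjects in a 1:1 ratio"). True HR 0.60, with 365 events at IA1 and 487 at the final PFS analysis (Table 20). One-sided alpha 0.2% and the spending rule from section 8.8: "A Hwang-Shih-DeCani (HSD) spending function with $\gamma = -2$ (α -spending for efficacy) is used to set efficacy bounds".

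**1. Alpha spent at IA1.** Information fraction t = 365/487 = 0.7495. HSD spending with gamma = -2 is alpha × (e^(2t) − 1)/(e^2 − 1) = 0.2% × 3.477/6.389 = 0.109%. The bound is Z = 3.065. Table 20 prints 0.11% and 3.06, so this reproduces.

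**2. Final bound.** Choose Z2 so that the total one-sided rejection probability under the null is 0.2%, with correlation √0.7495 = 0.866 between the two looks. Result: Z2 = 2.996, nominal alpha 0.137%. Table 20 prints 3.00 and 0.14%.

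**3. HR at the bounds.** exp(−2Z/√d) gives exp(−2 × 3.065/19.105) = 0.726 and exp(−2 × 2.996/22.068) = 0.762. Table 20 prints 0.73 and 0.76.

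**4. Drift under HR 0.60** (Schoenfeld). √(d/4) × |ln 0.60| = 0.2554 × √d, which is 4.880 at 365 events and 5.636 at 487.

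**5. Power at IA1.** Φ(4.880 − 3.065) = Φ(1.815) = 96.5%. Table 20 prints ~96.5%.

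**6. Power at the final analysis.** Type II error is the probability of staying below both bounds: the bivariate normal probability at (3.065 − 4.880, 2.996 − 5.636) = (−1.815, −2.640) with correlation 0.866. This is 0.377%, so cumulative power is 99.62%. With the printed, rounded bounds 3.06 and 3.00 the Type II error is 0.381%.

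**7. Same method on the neighbouring final rows.**

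| Row | Type II error, computed | Type II error, printed | Power, computed | Power, printed |
|---|---|---|---|---|
| PFS, 0.2% | 0.377% | ~3.9% | 99.62% | >99.9% |
| PFS, 1.35% | 0.041% | ~0.04% | 99.96% | >99.9% |
| PFS, 2.5% | 0.016% | ~0.02% | 99.98% | >99.9% |
| OS, 2.3% (printed bounds) | 19.1% | ~19.2% | 80.9% | ~80.8% |

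Of these rows, only the PFS row at 0.2% fails.

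**8. Could another convention produce the printed cells?**

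| Variant, alpha 0.2%, HR 0.60, 487 events | Power |
|---|---|
| Final look alone (marginal, not cumulative) | 99.59% |
| IA1 at the 305-event minimum instead of 365 | 99.64% |
| Freedman instead of Schoenfeld drift | 99.47% |
| Fixed design, one-sided 0.2% | 99.71% |
| Fixed design, two-sided 0.2% | 99.46% |

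None exceeds 99.9% and none falls to 96.1%. Stopping at the IA1 futility bound (Z −0.77) does not help either: under HR 0.60 it lies −0.77 − 4.880 = −5.65 standard deviations from the mean, so it adds essentially nothing, in line with the <0.01% printed there.

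**The case against.** The strongest reply is that nothing operative is wrong. The nominal alpha, Z-value and HR bound in this row all reproduce, and so does the IA1 row above it. The Type II column is descriptive. Section 8.7 says the table will be updated with actual event counts and that futility bounds are non-binding. Section 8.9 states that 861 subjects are already randomized, so no sample-size choice rests on this cell. Even on the wrong reading, 96.1% would be ample. All of that stands, and it limits the severity.

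A reader might also infer that the plan gives three incompatible power figures: about 99% in the text, >99.9% in the table, and 96.1% implied by the Type II error. The documents do not support that. The text figure carries an approximation sign and the design delivers 99.6%, so sections 8.1 and 8.9 are a fair, slightly conservative rounding. The conflict lies between two cells of one row.

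The footnote's silence on whether PFS power is cumulative might seem to leave room, but the marginal figure is 99.59%, which matches neither cell. Finally, Table 20 is easily broken in a text copy, where this row appears just above the IA2 label beside the ORR rows. Its nominal alpha, Z and HR identify it as the final PFS test at 0.2%, and its columns align with the two PFS rows below it. Checking the two cells against the PDF is still sensible.

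**Conclusion.** The internal contradiction is certain, since the two cells cannot both be true at a final analysis. On the stated design neither is right. The Type II error is 0.38% against ~3.9% printed, about ten times too large (3.9/0.38 ≈ 10). Power is 99.62% against >99.9% printed, an overstatement of about 0.3 points. A misplaced decimal would explain the Type II cell, and the power entry fits only the 1.35% and 2.5% rows, but the cause of either slip is inference.

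The derived values assume proportional hazards with HR 0.60, 1:1 allocation, the asymptotic log-rank approximation, and looks at 365 and 487 events. Moving IA1 to 305 events or changing the drift formula leaves the Type II error between about 0.36% and 0.53%.

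It would be wrong to infer that PFS is underpowered or that its boundaries are miscalculated: every boundary figure in the row reproduces and power is above 99%. This is a minor reporting error in the row for a primary endpoint at its initially allocated alpha.

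**What to change.** In Table 20, final PFS row at IA2 with alpha 0.2%, replace power >99.9% with ~99.6% and cumulative Type II error ~3.9% with ~0.4%. Leave sections 8.1 and 8.9 as they are. The cost is two table cells at the next amendment. One stated power becomes slightly less favourable; no boundary, alpha allocation, event target or analysis timing is affected.
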